## **1.11 Inclusion /Exclusion Criteria**

### ***1.11.1 Inclusion Criteria***

1. Males and non-pregnant/non-breastfeeding females at least 18 - 74 years of age.
2. Ability to comprehend the study procedures and signed informed consent.
3. Diagnosed with any the following: acute leukemia (ALL or AML), myelodysplasia, aplasia, and/or therapy (chemotherapy or radiation) induced bone marrow aplasia or hypoplasia with thrombocytopenia (see #6 below) for a minimum of 2 days. Patients who have received either autologous or allogeneic bone marrow transplant, peripheral, or cord blood stem cells may be enrolled if they do not have chronic or acute graft-versus-host disease (GVHD).
4. WHO Grade 1 (subset) or 2 bleeding or at risk for same within 4 weeks of screening. Subset of patients with Grade 1 bleeding are those who have either epistaxis, hematuria, oral petechiae, oropharyngeal bleeding, or bleeding at invasive or other wound sites. WHO Grades 0, 3 or 4 are not inclusion criteria for eligibility.
5. If not hospitalized, willing to be observed in a clinic up to the 6-hour post-infusion time point. Patients may be admitted and observed in the hospital overnight at the discretion of the PI.
6. Thrombocytopenia with platelet count  $\geq 5,000/\mu\text{L}$  and  $\leq 70,000/\mu\text{L}$ .
7. Has permanent address and phone/email for contact and notifications, and available for the duration of the trial, which is expected to be a maximum of 8 weeks.
8. Agrees to not take any nonsteroidal inflammatory drugs within 5 days prior to infusion and during the 6 Day study follow-up period.
9. Agrees to not take any aspirin or aspirin containing drugs within 5 days prior to infusion and during the 6 Day study follow-up period.

10. Agrees to not take any COX-2 inhibitor drugs within 5 days prior to infusion and during the 6 Day study follow-up period.
11. Female patients must have a negative pregnancy test prior to enrollment and during study. Women who are postmenopausal for at least 1 year (>12 months since last menses) or are surgically sterilized do not require this test.

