### **1.16 Data Analysis**

Separate data summaries will be prepared for each cohort:

- Demographic and medical history data will be summarized. For quantitative variables, summaries will include the sample size, mean, median, standard deviation, minimum, and maximum. For qualitative variables summaries include the number and percent of patients for each outcome.
- Exploratory analyses will include the observed response and the change from baseline to each of the post-infusion time points for each of the laboratory tests (hematology, coagulation, platelet and chemistry). Additionally, summaries of the number and percent of patients with both a change of  $>5\%$  from baseline and whose results are outside of reference ranges will be displayed. For quantitative variables summaries of the observed response and the change from baseline to each of the post-baseline time points will include the sample size, mean, median, standard deviation, minimum, and maximum. Additionally, for the change from baseline summaries, the statistical significance will be determined using either a t-test or the Wilcoxon Signed Rank test, as appropriate. Summaries for qualitative variables will include the number and percent of patients for each outcome.
- Incidence of AEs and SAEs per patient and by body system will be summarized showing the number and percent of patients for each outcome. Summaries will also be prepared by severity and relationship to treatment.
- Summaries of vital signs and clinical data including WHO bleeding scores will include the observed response and the change from baseline to each of the post-infusion time points for each of the variables. For quantitative variables summaries of the observed response and the change from baseline to each of the post-baseline time points will include the sample size, mean, median, standard deviation, minimum, and maximum. Additionally, for the change from baseline summaries, the statistical significance will be determined using either a t-test or the Wilcoxon Signed Rank test, as appropriate. Summaries for qualitative variables will include the number and percent of patients for each outcome.

A statistical analysis plan will be developed as part of the data analysis plan.

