## 1.18 Risk Assessment

### 1.18.1 *Foreseeable or Potential Risks*

The following risks to participation of this clinical trial are outlined in the Table 5 below:

Table 5. Potential Study Risks	
Trial Stage	Risks Identified
AEs Possibly Related or Related to Thrombosomes Infusion during Phase 1 Study No. 2011-1	

• Prothrombin Level Increased (Elevated Prothrombin Fragment 1+2)

• White Blood Cell Count Increased

• Fibrin D-dimer Increased

• Electrocardiogram T-wave Abnormal

• Autoantibody Positive (Platelet Autoantibody)

AEs Associated with Blood Product Infusion including Platelet Infusion which may also be associated with Thrombosomes	

• Hematoma or localized infection at the venipuncture site

• Nausea/vomiting, dizziness/ fainting, seizures

• Allergic reaction (flushing, itching, hives, abdominal cramps, difficulty breathing, chest pain, or bronchospasm, which may vary in severity from mild to life-threatening)

• Difficulty breathing, chest pain, or bronchospasm, which may vary in severity from mild to life-threatening)

• A minimal risk of cancer cannot be completely and definitely ruled out

• Immune suppression

• Infectious disease transmission

• Cardiac failure

• Noncardiac pulmonary edema

• Stroke

• Thrombocytopenia

• Formation of platelet antibodies

• Thrombosis – arterial or venous

• Pulmonary Embolism

• Heart attack

• Death

Miscellaneous	

• Breach of patient confidentiality

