### **1.22.6 *Adverse Events and Unanticipated Problems***

#### **1.22.6.1 *Definition of Terms***

##### **A. Adverse Event (or Adverse Experience):**

Any untoward medical occurrence in a patient administered a pharmaceutical product and which does not necessarily have to have a causal relationship with this treatment. An

adverse event (AE) can therefore be any unfavorable and unintended sign (including an abnormal laboratory finding, for example), symptom or disease temporally associated with the use of a medicinal product, whether or not considered related to the medicinal product.

An abnormal laboratory finding that requires medical or surgical intervention or leads to study treatment interruption or discontinuation must be recorded as an AE (or SAE, if applicable). If the changes from baseline are mild and in the opinion of the investigator not clinically significant, the event is not considered an AE, however, the investigator should continue to carefully monitor the values. Laboratory tests may be repeated, as clinically indicated, without prior approval by Sponsor or Medical Monitor. Special attention must be paid to the results of coagulation parameter results not within reference ranges.

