## 1 INTRODUCTION

This document outlines the methods of statistical analysis and data presentation associated with clinical study protocol (CSP) 2017-1, describing a Phase 1, multicenter, open-label, dose-escalation study. Within this study, the effects of escalating infusion doses of the investigational product, Thrombosomes®, will be assessed within a target population of actively-bleeding, thrombocytopenic patients (with platelet counts 5,000-70,000/ $\mu$ L). Patient inclusion will further be restricted to those with modified World Health Organization (WHO) bleeding severity scores of grade 1 (including only those patients with epistaxis, hematuria, oral petechiae, oropharyngeal bleeding, or bleeding at invasive or other wound sites) or grade 2, with bleeding due to hematologic/oncologic disease or bone marrow aplasia secondary to chemotherapy or radiotherapy. While the overall study design, study objectives and endpoints, and proposed methods for manipulating, analyzing, and presenting data are described below, the reader is referred to the CSP and case report forms for detailed descriptions of the investigational product, full list of patient inclusion/exclusion criteria, and data collection methods.

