## 2.2 Study Endpoints

### 2.2.1 Primary Endpoints

Several primary endpoints will be quantified per patient cohort (i.e., by dose level), as well as overall (i.e., across all 3 dose levels):

- Overall frequency of (and number and percentage of patients who experience) TEAEs and TESAEs, including serious adverse drug reactions and treatment-related events specifically defining the study's suspension and stopping rules (i.e., thromboembolic events, acute lung injury, anaphylaxis, and death).
- Numbers and percentages of patients by highest WHO bleeding severity grade at baseline and post-baseline time-points, by highest severity grade at post-baseline time-points relative to baseline (allowing for assessment of shift), by both highest severity grade and bleeding site at baseline and post-baseline time-points, and by indication of a maximum severity grade  $\geq 2$  across bleeding sites at post-baseline time-points.
- Numbers and percentages of patients by grade-level change in WHO bleeding severity (e.g., -2, -1, 0, +1, +2, +3) from baseline to post-baseline time-points for the patient's most severe bleeding site at baseline, by indication of increased bleeding severity from baseline to post-baseline time-points for the patient's most severe bleeding site at baseline, and by indication of newly-developed bleeding sites from baseline to post-baseline time-points.
- Statistics describing (and/or graphics showing) central tendency and variability in coagulation, hematology, and serum chemistry measures across patients at baseline and post-baseline time-points, allowing for assessment of directional change in measures over time.
- Number and percentage of patients who shift from normal or clinically non-significant abnormal findings to clinically significant abnormal findings in coagulation, hematology, or serum chemistry measures between baseline and post-baseline time-points.
- Statistics describing central tendency and variability in vital signs, oxygen saturation (per pulse oximetry), and select 12-lead electrocardiogram (EKG) measures across patients at baseline and post-baseline time-points.
- Number and percentage of patients who shift in category of overall EKG interpretation from normal or clinically non-significant abnormal to clinically significant abnormal between baseline to post-baseline time-points.

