### 8.3 Clinical Laboratory Assessments

Laboratory assessments to be used in safety monitoring will include coagulation, hematology, and serum chemistry measures. For each assessment type, descriptive statistics summarizing the raw and CFB values of all measures (or select measures, see Hematology below) will be provided in 2 tables. As the Wilcoxon signed rank test will be used to test for difference between baseline and post-baseline values, the P-values derived during testing will be displayed within these tables, adjacent to corresponding CFB values. In 2 additional tables, the numbers and percentages of patients who show abnormal results and who show changes (shifts) from baseline in interpreted results (normal, abnormal non-clinically significant, and abnormal clinically significant) will be summarized per measure and visit. Measures corresponding to each assessment type will include those listed below, given sufficient data available for descriptive analysis (i.e., minimally 3 data points per computed statistic for each of 2 or more visits).

- **Coagulation:** PT, INR, aPTT, D-dimer, fibrinogen, TAT, PF 1+2, TEG (R time, K time, MA, angle), ROTEM (CT, CFT, angle, MCF), and TGA (lag time, time to peak, thrombin peak height, ETP)
- **Hematology:** WBC, RBC, hemoglobin, hematocrit, platelets, MPV, neutrophils, lymphocytes, monocytes, eosinophils, and basophils
  - Descriptive summaries of raw values will be presented in a single table for the select measures of WBC, RBC, hemoglobin, hematocrit, platelets, and MPV.
  - Descriptive summaries of CFB values and Wilcoxon signed rank test results will be presented in a single table for the select measures of WBC, neutrophils, lymphocytes, monocytes, eosinophils, and basophils.
- **Chemistry:** blood glucose, BUN, creatinine, sodium, potassium, chloride, calcium, CO2, alkaline phosphatase, AST (SGOT), ALT (SGPT), total bilirubin, GGT, albumin, LDH, total cholesterol, total protein, and hs Troponin I (or hs Troponin T)

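### The laboratory shift endpoint cannot count worsening in a patient already labelled clinically significant at baseline, and the SAP states no at-risk denominator and does not separate low from high

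*SAP*

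**What the plan says.** SAP 2.2.1 lists as a primary endpoint the "Number and percentage of patients who shift from normal or clinically non-significant abnormal findings to clinically significant abnormal findings in coagulation, hematology"; it also covers serum chemistry, and compares baseline with later time-points. SAP 8.3 carries this out with tables in which "changes (shifts) from baseline in interpreted results (normal, abnormal non-clinically significant, and abnormal clinically significant) will be summarized per measure and visit". Neither section states a denominator, gives a rule for when a value is clinically significant, or divides abnormal into low and high.

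Inclusion criterion 6 in Protocol 1.11.1 is "Thrombocytopenia with platelet count" from 5,000 to 70,000/µL. Criterion 3 limits entry to acute leukemia, myelodysplasia, aplasia, or marrow aplasia or hypoplasia caused by therapy. SAP 2.1.1 names worsening in hematology among the indicators of safety.

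Three other provisions bear on the point:

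- The hematology change-from-baseline table in SAP 8.3 covers WBC and the differential counts. Platelets, hemoglobin and hematocrit appear only in the raw-value table.
- SAP 9.1 defines worsening as a fall of 5,000/µL in platelets, 1 g/dL in hemoglobin or 3% in hematocrit. It does so as an efficacy summary, and a patient who both worsens and improves is classed as improved.
- Protocol 1.16 plans the "number and percent of patients with both a change of" more than 5% and a result out of range. SAP 8.3 does not use this summary, and SAP 11 does not list its removal.

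**The concern.** The endpoint is a one-way move into the worst category. A patient who starts there has nowhere to go, and if he or she stays in the denominator, the reported percentage has a ceiling below 100% that the reader cannot see. This population makes that likely for some patients: all are thrombocytopenic at entry, and Protocol 1.9.3 anticipates leukopenia and anemia from the underlying disease.

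The categories also have no direction. A move from a clinically significant low value to a clinically significant high one shows as no shift. Protocol Table 5 lists "White Blood Cell Count Increased" among the events at least possibly related to the product in the first study, and thrombocytopenia among the risks of blood product infusion.

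At stake is how a low count of shifts is read. No shifts among 8 patients means one thing if all 8 could have shifted and another if only 2 could.

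**Working it through.** The documents give no power, effect size or event rate for this endpoint, and SAP 4 says the sample size was not statistically derived. There is therefore no planned figure to reproduce. What follows illustrates the size of the gap.

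**Inputs.** N = 8 per cohort (SAP 4). q is the share of patients already labelled clinically significant at baseline for a measure. The documents do not give q, so it is assumed to lie anywhere from 0 to 100%. A true shift rate of 20% among patients at risk is a further assumption, for illustration.

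**Formulas.** Patients able to register: n = N(1 − q). Probability of at least one shift: 1 − (1 − 0.20)^n. Exact two-sided 95% upper limit when no shift is seen: 1 − 0.025^(1/n).

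| q | n of 8 | Highest possible % on a denominator of 8 | P(at least one shift) at 20% | Upper limit for 0/n |
|---|---|---|---|---|
| 0 | 8 | 100% | 1 − 0.8^8 = 83% | 1 − 0.025^(1/8) = 37% |
| 25% | 6 | 75% | 1 − 0.8^6 = 74% | 1 − 0.025^(1/6) = 46% |
| 50% | 4 | 50% | 1 − 0.8^4 = 59% | 1 − 0.025^(1/4) = 60% |
| 75% | 2 | 25% | 1 − 0.8^2 = 36% | 1 − 0.025^(1/2) = 84% |
| 100% | 0 | 0% | 0% | no information |

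If four patients were at risk and none shifted, a table printing 0/8 would suggest an upper limit of 37%, when the data support only 60%.

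**What else could show a fall.** Raw platelets, hemoglobin and WBC are summarized by visit and plotted for each patient (SAP 8.3), and falls can be reported as adverse events. These do show worsening. But the raw summaries and plots give no count of patients who worsened, and the change table leaves out platelets and hemoglobin. The 9.1 categories do give a count whatever the baseline label, but the override weakens it: Protocol 1.9.2.2 allows transfusion for unchanged or worsening bleeding, so a platelet fall followed by a transfusion-related rise can be reported as improvement.

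**Limits of the 9.1 platelet threshold as a safety count.** A fall of 5,000/µL is 5,000/5,000 = 100% of the lowest eligible baseline, 5,000/20,000 = 25% at 20,000, and 5,000/70,000 = 7.1% at the highest. It is barely reachable at the bottom of the range and small enough to be ordinary variation at the top.

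**The case against.** A reader might infer that worsening platelets cannot register in anyone, and that the endpoint will show about zero platelet shifts whatever the product does. The documents do not support this. It is true only at q = 100%, and neither document says that a count of 5,000-70,000/µL is clinically significant. The label is an interpretation. The protocol's adverse event definition (1.22.6.1) ties it to change from baseline: if changes are mild and "in the opinion of the investigator not clinically significant, the event is not considered an AE". A count expected from the disease may be labelled non-significant at baseline, and a later fall could then count. For hemoglobin and WBC the documents give no baseline criteria at all.

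It is also fair to say that the denominator is unstated, not stated wrongly. A conventional baseline-by-visit layout of Table 14.3.5.4 would reveal how many patients began as clinically significant, but the table shell is not in the documents.

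Other routes exist. The endpoint just before this one in SAP 2.2.1 covers directional change in the same measures. Laboratory abnormalities that need intervention must be recorded as adverse events. A WBC reversal would be visible in its change-from-baseline table, the individual plots and the WBC-level table, so the missing direction is a fault of the shift table and does not hide the event.

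Finally, suspension and stopping depend on related serious adverse events, and the DMC receives adverse event tables and a hematology listing. No decision rule uses the shift count.

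All of this stands, and it limits the importance of the point. It does not remove the structural gap for patients labelled clinically significant at baseline, or the two weaknesses in the back-up.

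**Conclusion.** The point holds for this endpoint and not for safety monitoring as a whole. For any measure, patients already labelled clinically significant at baseline cannot contribute a shift, the SAP does not confine the percentage to the others, and a change from low to high is lost. The size depends on q, which the documents do not give: from no loss at q = 0 to no information at q = 100%, with half of each cohort lost at q = 50%. The 37%, 60% and 84% limits are exact for zero events in 8, 4 and 2 patients. Which of them applies is unknown until baseline labels are tabulated.

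This is an inexpensive improvement to the safety tables. It is not a defect that endangers the trial's conclusions. It is worth making because SAP 2.1.1 counts hematology worsening as a safety indicator, while the one patient-level count of worsening that ignores the baseline label sits in the efficacy section and can be cancelled by a later rise.

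**What to change.** Amend SAP 2.2.1 and 8.3, and Tables 14.3.4.4, 14.3.5.2, 14.3.5.4 and 14.3.6.4:

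1. Report shift percentages among patients not already clinically significant at baseline for that measure, and print that number.
2. Split abnormal into low and high, so that reversals are seen.
3. Report the SAP 9.1 worsening counts for platelets, hemoglobin and hematocrit as a safety summary as well, per visit, whatever the baseline category and without the improvement override. Show them descriptively beside baseline values, because the absolute platelet threshold is hard to reach from the lowest baselines and within noise at the highest.
4. Add platelets, hemoglobin and hematocrit to the change-from-baseline table (14.3.5.2).

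The cost is SAP wording and a few table rows, with no new data. The downside is that some counts under item 3 will reflect ordinary variation, which is why they should carry no test or decision rule.

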### 2.2.2 Secondary Endpoints

Multiple secondary endpoints will be quantified per patient cohort (i.e., by dose level), as well as overall (i.e., across all 3 dose levels):

- Number and percentage of patients who, from baseline to post-baseline time-points, show either stability (i.e., no change) or an intermittent or sustained change toward clinical improvement in hematology measures, with or without reaching normal levels.
- Number and percentage of patients who receive transfused blood products following infusion.
- Statistics describing central tendency and variability in the numbers of units of blood products transfused following infusion.

### 3 STUDY DESIGN

#### 3.1 Overall Design and Patient Participation

This study is a Phase 1, multicenter, open-label, dose-escalation study with a target study population of bleeding, thrombocytopenic patients. Patients from this population who show modified WHO grade-1 or grade-2 bleeding severity due to hematology/oncology diseases or bone marrow aplasia secondary to cancer chemo/radiotherapy will be enrolled and treated with the investigational product, Thrombosomes. Three cohorts of 8 patients each (for a total of 24 patients) will be sequentially enrolled, corresponding to 3 escalating infusion doses of Thrombosomes (5 mL [ $9.45 \times 10^7$  particles/kg or 165 TGPU/kg], 10 mL [ $1.89 \times 10^8$  particles/kg or 330 TGPU/kg], and 20 mL [ $3.78 \times 10^8$  particles/kg or 660 TGPU/kg]). The timing (or order) of patient enrollment, consequently, will dictate the dose level assignment of individual patients (see **Table 1**). Moreover, doses will be adjusted for patient weight.

**Table 1 – Patient Cohort Assignment, Target Dose, and Safety Margins**

Cohort	No. of Infusions	Target Mean Particles/kg	Target Mean TGPU/kg	Estimated Total Volume Infused 	Safety Margin 	
					Infused Particles/kg	Infused TGPU/kg
Cohort 1 (patients 1-8)	1	$9.45 \times 10^7$	165	4.1 mL	300	301
Cohort 2 (patients 9-16)	1	$1.89 \times 10^8$	330	8.2 mL	150	150
Cohort 3 (patients 17-24)	1	$3.78 \times 10^8$	660	16.4 mL	75	75

Abbreviation: TGPU, thrombin generation potency units.

 Estimated Total Volume Infused is based on a 70-kg patient and mean Thrombosomes concentration (across lots) of  $1.61 \times 10^9$  particles/mL with associated 2,800 TGPU/mL. Doses will be adjusted by patient weight in order to maintain the target Thrombosomes particle count per kg of patient body weight. Formula: Total Volume Infused in mL = ([patient weight in kg] x [desired dose in particles/kg or TGPU/kg, specific for the cohort]) ÷ Thrombosomes particles/mL or TGPU/mL provided with the specific lot of Thrombosomes. Example for Cohort 1: 4.1 mL = ([70 kg] x [ $9.45 \times 10^7$  particles/kg]) ÷  $1.61 \times 10^9$  particles/mL.

 Safety margins are based on the single acute toxicity study in New Zealand white rabbits (see CSP Section 1.7).

Written informed consent will be obtained from patients who are either actively bleeding or at risk of bleeding within 4 weeks following screening. Patients who are actively bleeding and determined through screening assessments to meet eligibility criteria for study participation will be immediately scheduled for infusion with Thrombosomes to occur within 4 days of screening. Patients who are not actively bleeding during screening but are at risk for bleeding within 4 weeks, based on medical history and projected clinical course, will be monitored for bleeding. If bleeding begins within 4 days (+6 hours), complete rescreening will not be necessary, but updated WHO bleeding assessment and complete blood count (CBC) tests will be required for determination of eligibility. If bleeding begins >4 days later but within 4 weeks of initiation of screening, rescreening (inclusive of all original screening assessments) will be necessary for

determination of eligibility. Given determination of eligibility through either scenario (i.e., completion of updated screening or rescreening assessments), the patient will be immediately scheduled for infusion with Thrombosomes to occur within 4 days. Patients who are not infused within 4 days of eligibility determination will (re-)enter rescreening, if no more than 4 weeks have passed since initiation of screening. Patients who are not infused within 4 weeks of initiation of screening will no longer be actively monitored for study eligibility or scheduled for infusion. However, they may subsequently re-enter the screening process at any time, if actively bleeding or determined to be at risk of bleeding. Patients will be classified as enrolled in the study at the onset of infusion.

Activities and assessments relating to the pre-infusion (screening) period, infusion (Day 1), and the post-infusion period (follow-up through Day 30 +2 days) will be performed as indicated in **Table 2** (see Section 3.3, Summary of Activities and Assessments). Importantly, stipulations exist concerning patient enrollment and the performance of assessments. For instance, patient infusions cannot occur on the same day. Once an eligible patient has been infused, the patient must reach Day 4 without a suspension or stopping rule event being reported before a subsequent patient may be infused (see Section 3.2, Safety Assessments). In addition, a 2-week interval of non-enrollment (i.e., no infusions), with all patients on study having completed the planned Day-6 follow-up visit (on Day 6 +4 days), must be met between cohorts to allow for an independent Data Monitoring Committee (DMC) to review all safety data from the previous cohort and provide recommendations on whether the study should advance to the next cohort (see **Appendix 1**).

The duration of each patient's participation in the study is expected to be approximately 4-8 weeks. Patients will be deemed "evaluable" after completing the planned Day-6 follow-up visit (on Day 6 +4 days) and considered to have completed the study after completing the planned Day-30 follow-up visit (on Day 30 +2 days). Time from first patient/first visit to last patient/last visit is expected to be 12 months. While the Investigators will make every effort to maintain patient participation through study completion, patients will be permitted to withdraw their consent for participation at any time, and circumstances may arise supporting the decision of the Investigator(s) to terminate the patient's participation, including:

- Non-compliance (e.g., no-show for scheduled visit, impairment due to drugs/alcohol, agitation/disruption during visit, inability to follow clinic rules concerning conduct)
- Safety issues (e.g., patient does not meet inclusion criteria for ongoing stages of the study, clinic safety due to unacceptable conduct, study cancelled due to product safety)
- Sponsor-initiated study termination
- Investigator-initiated study termination
- IRB of record or FDA study termination

